3.3. Primary outcome measures

Objective A), i.e. whether children have learned a shape bias, will be assessed by means of a noun extension test with novel names and objects never heard and seen before by the infants at the end of the intervention programme.

Objective B), i.e. whether the intervention programme benefits infants' general vocabulary development, will be assessed with a vocabulary checklist filled in by the parents/guardians before and after both types of intervention. We will compare the vocabulary growth in the group of children that took part in the shape bias intervention programme with that of the group of children that took part in the 'specific word' intervention. A significant larger increase in the shape bias intervention compared to the 'specific word' intervention will provide information regarding the success or efficacy of the shape bias intervention.

Objective C), i.e. whether the shape bias intervention has a "long-term" effect on language development and cognitive abilities. Receptive and expressive language, and cognitive abilities, such as visual spatial skills and working memory, will be assessed at one year after the end of the intervention programme.

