4.3. Tests and procedure of intervention programme

4.3.1. Vocabulary and developmental assessments. At session 1, parents/guardians will fill in a socioeconomic and general development questionnaire (see Appendix 1.5). The

information provided in this questionnaire will double-check the inclusion/exclusion criteria. It will also be used to check whether the intervention was only successful in a sub-group of the infants (e.g. those without a family history of language problems). In the first and last session, parents/guardians will also be asked to fill in the UK-CDI Words and Gestures questionnaire, a vocabulary checklist of words and phrases that infants might know and use (Alcock, Meints, & Rowland, 2017; see Appendix 1.4). This will allow us to compare language development during the intervention programme between the two intervention groups.

4.3.2. Initial cognitive assessments: The initial cognitive assessments will be presented during the first two sessions. During week 1, infants will be assessed with a shape sorting task and an attention task. The sorting task will last no more than 5 minutes and will be used to assess if before the training programme, infants are sensitive to the shape of objects and can group objects by shape. Infants will be presented with 16 novel objects differing in shape, colour and texture and asked to sort them into groups. How to sort (namely by shape) will be shown to them with the means of examples. The attention task will last 3 minutes and will assess infants' joint and sustained attention. This will be achieved by monitoring their eye movements during the presentation of five short video clips (35 seconds each) of a person looking at and moving unusual novel objects. For this task, participants will sit on their parent/guardian's lap in front of a computer screen. Eye movement will be monitored with a remote eye tracker (see Figure 2). The parent will wear blacked-out glasses so that their behaviour cannot affect the infants' eye gazes.

At week 2, infants' visual spatial abilities and working memory will be assessed using the Wechsler Preschool & Primary Scale of Intelligence - Fourth UK Edition (WPPSI-IV UK). This test will last about 20 minutes and will be used to rule out any potential cognitive delay.

Figure 2. Attention task. Infants will watch five short videos and eye movements will be monitored with a remote eye tracker.

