5.5 Risk assessment

Participating in this research study does not represent a greater risk than what infants are exposed to in their everyday environment. The stimuli used are toy-like objects made from paper, clay, and string, the videos are short and age appropriate, and the procedures imitate play sessions. Even though the tasks are child-friendly and interesting, children will be encouraged to continue performing a task if they do not seem motivated. If positive encouragement fails or the child seems uncomfortable or distressed, the researcher will stop the task and/or session, and will give the child his/her reward. The session might be rescheduled if deemed useful and with the approval of the parent/guardian.

The tasks require the child to sit on the parent's/guardian's lab, on a child's chair or on the floor, which will minimize the risk of any falls. The testing area will be child-friendly (eg. electrical sockets covered) and small objects or objects that are not safe for a small child (e.g. scissors, medicines) will be removed from the room prior to the arrival of the participants. Some children might suffer from food allergies, and as in consequence, any food (like biscuits or tea offered to the parents) will be kept in a secure place away from the children. Parents will be present at all times and it will be ensured that all researchers have undergone a DBS check for working with children.

Due to the constant contact between researcher and children, there is a minor risk of contagious diseases such as colds or stomach bugs. In order to minimize the risk, the researcher will wash their hands before and after each session with alcohol based hand wash, and all items that the child might touch, such as toys, chairs and tables, will be cleaned and disinfected after every session. There are no risks to the environment or society arising from this research.

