6.3.1 Summary of baseline data

From the total number of assessments and tasks, results from five of them will be used as baseline data or descriptive statistics. These five assessments are: Vocabulary checklist, Socioeconomic and general development questionnaire, attention task, sorting task, initial working memory assessment, and initial visual spatial abilities assessment. The description of the variables analysed on each assessment and how they will be reported is as follows.

- A. Vocabulary assessment: Parents will fill out this checklist before (and after) the intervention and the total number of words that the infant understands and the total number of words they

produce will be registered as continuous variables and will be considered as the baseline language ability before the intervention programme.

- B. Socioeconomic and general development questionnaire: This questionnaire will provide information regarding general child development, language delay family history, and family status. A number of different types of variables will be collected: nominal variables (e.g. occupation) and ordinal variables (e.g. infant's order of birth). These variables will be used for descriptive statistics. They are potentially interesting as predictor variables, but the sample size is likely too small to draw any strong conclusions.
- C. Attention measure: With this measure, we will assess the fixation duration (number of milliseconds an infant looks) towards a novel object that is moved. The object will be moved for 25 seconds (25000 ms) and the infant's total looking time towards the screen will be registered. This variable will be registered as a continuous variable and used as a predictor of the primary outcome measures.
- D. Sorting task: This will be registered as a categorical variable. Infants will sort objects and depending on their sorting tendency they will be assigned to one of four categories: preference for shape, preference for colour, preference for texture, no preference. This variable will be used as a predictor of the primary outcome measures.

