6.3.2 Primary outcome analysis

During weeks 8 and 9 of the study infants will be assessed with two forced choice tasks where they will have to extend object names to new exemplars based on visual commonalities. We will assess the statistical difference between the response pattern and chance (using t-tests). This will show whether infants have learned to extend object names by shape similarities. The factors that predict the number of noun extensions based on shape as well as vocabulary growth will be assessed using mixed effect model analyses. The most important factors tested in the models will be the number of words known before the intervention, the intervention type (shape training vs specific word training), attention measures (pre-test and attention during training), and sorting task measure. The outcome of these analyses will show whether the shape bias intervention has led to a larger vocabulary growth than the specific word intervention (as a control intervention). It will also assess the role of attention in word learning and whether only infants that pay attention to novel items

presented to them or infants that are sensitive to shape similarities between objects can acquire a shape bias. Only data of infants that complete the intervention will be analysed.

Regarding the follow up study, infants' vocabulary and cognitive abilities will be assessed. This with the aim of analysing if there are any long-term effects of each intervention and infants continue learning words and potentially "catching up", or if the intervention programmes are only beneficial while they are being implemented. The cognitive assessments will be used to assess whether the intervention has an effect on visual spatial skills and working memory. In both cases, it will be done by comparing the infants results to the standardized mean of UK infant population. Similarly, infant's result in the follow up language assessment will be compared to the standarized mean of UK infant population.

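### The vocabulary-growth models list attention and sorting scores as factors with no rule for a missing score, so a usual complete-case fit would lose infants who have both checklists

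*Combined protocol and SAP*

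**What the plan says.** All references are to the combined protocol and SAP.

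- **Objective B (3.3).** "We will compare the vocabulary growth in the group of children that took part in the shape bias intervention programme" with growth in the specific word group. The data needed are the two parent checklists (4.3.1): "In the first and last session, parents/guardians will also be asked to fill in the UK-CDI Words and Gestures questionnaire".
- **Model (6.3.2).** Noun extensions by shape "as well as vocabulary growth will be assessed using mixed effect model analyses". One factor list serves both outcomes: "The most important factors tested in the models will be the number of words known before the intervention", then intervention type, then "attention measures (pre-test and attention during training), and sorting task measure". The section says these analyses will answer the vocabulary-growth question and gives no other between-arm analysis for it.
- **Role of the scores (6.3.1).** Of the attention score: "This variable will be registered as a continuous variable and used as a predictor of the primary outcome measures". The sorting category has the same role. It has four levels, one of which is no preference.
- **How the scores arise (4.3.2, 5.5).** Sorting and pre-test attention are child tasks in week 1. For attention, "Eye movement will be monitored with a remote eye tracker". Section 5.5 allows a task to end early: "If positive encouragement fails or the child seems uncomfortable or distressed, the researcher will stop the task and/or session". The session may then be rescheduled, but this is not guaranteed.
- **Population (6.3, 6.3.2).** The only written exclusion is failure to complete the intervention.
- **Missing scores.** There is no complete-case rule, imputation, missing indicator or reduced model.

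**The concern.** A mixed model can use an infant with a missing outcome record, but it has no built-in way to use an infant with a missing covariate. Unless the plan says otherwise, the usual fit drops that infant. The outcome here is a parent checklist, which can be complete even when a child would not sit for the eye tracker. A primary comparison could therefore lose infants with full outcome data because of measures that serve secondary Objectives D and E.

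Two things are at stake. One is precision, in a trial planned around 24 completers. The other is who remains: if tasks are stopped mainly for less cooperative or less attentive children, the arm comparison is made in a selected subset of completers.

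**Working it through.** **1. The plan's own figure.** Section 6.1 gives 24 completers for power 0.8, a medium effect and error probability 0.05. It names no test, sidedness, number of measurements or correlation, so these inputs do not determine a sample size. Taking medium in its conventional sense (an assumption: d = 0.5 or f = 0.25):

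- two-sample t-test, two-sided: 64 per arm;
- group-by-time interaction, 2 measurements: 34 in total at correlation 0.5, 22 at correlation 0.7;
- group-by-time interaction, 4 measurements, correlation 0.5: exactly 24 (power 0.816).

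The 24 is reachable, but only with inputs the documents do not give. It is neither confirmed nor refuted.

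**2. The recruitment margin.** 24 / 0.80 = 30. This matches a 20% allowance for infants who do not finish, the only reason section 6.1 gives for the margin. Nothing is set aside for completers without a covariate.

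**3. Does the listed model lose infants?** In a simulated data set of 24 infants, 4 lacked at least one of the two scores. A regression on group and baseline words used all 24. Adding attention and sorting left 20. A mixed model on complete rows used 40 of 48 records.

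**4. Size, by scenario.** Let f be the share of completers with no usable score. The documents do not give f, so the values below are assumptions. Infants left = 24(1 − f), and the standard error is multiplied by 1/√(1 − f).

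| f | Infants left | SE factor |
|---|---|---|
| 10% | 24 × 0.9 = 21.6 | 1/√0.9 = 1.05 |
| 20% | 24 × 0.8 = 19.2 | 1/√0.8 = 1.12 |
| 30% | 24 × 0.7 = 16.8 | 1/√0.7 = 1.20 |

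Losses from two tasks add up. If each fails independently with probability p, the share lost is 1 − (1 − p)²: 9.8% for p = 5%, 19% for p = 10%, 36% for p = 20%.

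**5. The same losses as detectable effect.** For a two-sided two-sample t-test at 0.05 with equal arms (the allocation ratio is not stated), the effect detectable with 80% power is 1.20 SD at 24 infants, then 1.27, 1.36 and 1.46 SD at 21.6, 19.2 and 16.8. The 1.20 is back-solved from 12 per arm. It is not the protocol's effect size and shows only relative change.

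**6. Dependence on the number of completers.** If 27 infants complete, a 10% loss leaves 24.3. If all 30 complete, a 20% loss leaves 24. The analysed number falls below 24 only if non-completion and missing scores together use up the margin.

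**The case against.** A reader might infer that the plan excludes an infant who does badly on either task. It does not, and four points on this side stand.

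- **No written deletion rule.** The stated exclusion is non-completion, and an infant who completes with both checklists is inside that population. Deletion is the default behaviour of the fit. What the plan lacks is the rule that would prevent it.
- **A poor result is not a missing one.** A child who shows no sorting preference has a valid category, and a child who looks briefly has a valid looking time. Only a task not done, or lost tracking data, leaves a gap. Tracking can also fail for technical reasons, so selection of the least attentive is possible but not shown.
- **Rescheduling may recover some scores.** Section 5.5 allows it.
- **Power figures cannot be read as this trial's.** The failure rate is unknown, the effect size in section 6.1 has no number, and at least 30 infants are to be recruited, so a fall below 24 is conditional.

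One further argument carries less weight. Section 6.3.2 calls these factors tested in the models, so the final vocabulary model might omit them. But section 6.3.1 makes both scores predictors of the primary outcome measures, section 6.3.3 describes them as entered in the model, and no model without them is specified for Objective B.

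**Conclusion.** The point holds as a gap in the specification of a primary comparison. The only between-arm model given for Objective B lists covariates that Objective B does not need and that can be missing, and the plan does not say how an infant without a score is to be handled. Under a complete-case fit, 10% to 30% of completers without a score would raise the standard error by about 5% to 20%, possibly with selection. These sizes rest on assumed failure rates and a start from exactly 24 completers; the true loss is unknown and could be close to nil.

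The same factor list also includes attention during training. It is a further possible source of missing values. It is also measured after randomisation and may be affected by the arm, so adjusting for it could distort the intervention effect even if no score were missing.

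**What to change.** In section 6.3.2:

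1. Estimate Objective B from intervention type and baseline words, in every infant with a baseline and a final checklist.
2. Keep attention and sorting for the Objective D and E models, and state there how missing scores are handled.
3. If pre-test attention or sorting is kept as a baseline covariate for Objective B, fill a missing attention score with the mean over both arms plus a missing indicator, and give sorting a separate missing category, which serves as its own indicator. These terms cost parameters in a model of about 24 infants, so option 1 is simpler.
4. Leave attention during training out of the Objective B model in either case.
5. Report, by arm, how many infants lack each score and why.

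The cost is SAP wording only, with no new data. The downside is a possible small loss of precision if the dropped baseline scores predict vocabulary growth.

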4.2. Study design

Infants will be randomly allocated to one of two groups: shape training group or specific word training group. Over a series of 9 weekly sessions, all infants will be assessed on different tasks that can be divided into 5 stages: Vocabulary and developmental assessments, initial cognitive assessments, training sessions, first-order generalization test, higher-order generalization test. Depending on the group that the children will be in, they will receive either a shape training or a specific word training. Other assessments (initial assessments, cognitive assessments, first-order generalization test and higher-order generalization test) will be identical across the groups. Additionally, a follow up study will be conducted after one year of completion of the intervention programme. A table describing the intervention procedure is provided in Figure 1. Details of the tasks are given below.

[figure not shown]

Figure 1. Timeline of intervention programmes.

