5.4 Indemnity and Participants payment

Parents will be offered reimbursement for travel expenses for every session that they attend at the Infant and Child Laboratory. Infants will receive a sticker every session they attend and will also receive a book or toy worth not more than £5 after attending all nine sessions.

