6.1 Sample size calculation

We are aiming to recruit and test 30 participants. This number is based on similar studies that have assessed language development in children. Additionally, a formal size calculation was used. The calculation showed that in order to achieve a power of 0.8 with a medium effect size and an error probability of 0.05, (a minimum of) 24 participants that finish the study needed to be recruited. Considering that some participants might not finish the whole study and their data might be used, we will aim to recruit at least 30 participants.

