6.3 Statistical analysis plan

Only data of infants that have completed the intervention will be fully analysed. Nevertheless, when possible, the total population assessed and the reason why certain participants did not finish the study (e.g. decided to withdraw, moved away, stopped attending) will be noted and reported in the study report. A full analysis of the data will be conducted once all data has been collected, which we anticipate to be after about 1 year of commencement of the study.

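### The randomised comparison of vocabulary growth keeps only infants who complete an undefined intervention, and the final checklist is tied to the last session, so selective loss can bias it

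*Combined protocol and SAP*

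**What the plan says.** Section 4.2: "Infants will be randomly allocated to one of two groups: shape training group or specific word training group". The programme runs over nine weekly sessions.

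The analysis set is given twice. Section 6.3 has "Only data of infants that have completed the intervention will be fully analysed", and section 6.3.2, which covers the primary outcomes, has the unqualified "Only data of infants that complete the intervention will be analysed". Section 6.3 also undertakes to report, where possible, the total assessed and "the reason why certain participants did not finish the study". It does not say that loss will be shown by arm. No section gives an as-randomised set, a missing-data method or a sensitivity analysis.

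Section 6.1 sits uneasily with this: "Considering that some participants might not finish the whole study and their data might be used".

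Completion is not defined. Section 5.4 gives infants a small reward "after attending all nine sessions", but that is a reward rule. Section 5.5 foresees sessions that are stopped, and then: "The session might be rescheduled if deemed useful and with the approval of the parent/guardian". It does not say how a stopped session that is never rescheduled counts.

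On the outcome for Objective B, section 4.3.1 says: "In the first and last session, parents/guardians will also be asked to fill in the UK-CDI Words and Gestures questionnaire". The one-year follow-up in section 4.4 lists the BPVS3 and WPPSI-IV, with no repeat UK-CDI.

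**The concern.** Randomisation makes the arms comparable at entry. Selecting on something that happens afterwards can undo this. Objective B rests on the intervention-type term in the mixed models of section 6.3.2. If the minimum in section 6.1 is just met, that term is estimated from 24 infants who stayed.

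The two trainings look different to a parent in the room: invented names in one arm, everyday words in the other. Reasons for stopping could therefore differ by arm. That is an inference; the documents give no data on it. Because loss by arm is not among the planned reports, a reader could not check.

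Two features make this worse. With completion undefined, whether an infant who missed a session is in or out could be decided after results are known. And the UK-CDI is filled in by the parent, so tying it to attendance loses data that could be obtained without the child.

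**Working it through.** **The plan's own figures.** Section 6.1 needs 24 finishers and recruits 30. The implied loss is 30 − 24 = 6, or 6/30 = 20%, and 24/(1 − 0.20) = 30. The plan does not state this rate. How 24 was obtained is a separate matter and does not affect this point.

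**Assumed inputs.** Allocation 15:15, 6 infants lost, no true difference, growth in SD units. Within an arm, the infants lost are the k lowest on a propensity to stay that correlates r with growth. None of this is in the documents.

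**Formula.** Let S_k be minus the sum of the k lowest expected normal order statistics for n = 15: S_1 = 1.736, S_2 = 2.984, S_3 = 3.932, S_4 = 4.646, S_5 = 5.162, S_6 = 5.497. The completers' mean in an arm that loses k is shifted by r × S_k/(15 − k). The bias is the difference between the arms' shifts.

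- 4:2: 4.646/11 − 2.984/13 = 0.193, times r
- 5:1: 5.162/10 − 1.736/14 = 0.392, times r
- 6:0: 5.497/9 = 0.611, times r
- 3:3, low growers lost in one arm and high growers in the other: 2 × 3.932/12 = 0.655, times r

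| Loss | r = 0.3 | r = 0.5 | r = 0.7 | Type I error, r = 0.5 (0.7) |
|---|---|---|---|---|
| 4:2 | 0.06 SD | 0.10 SD | 0.14 SD | 6.5% (7.9%) |
| 5:1 | 0.12 SD | 0.20 SD | 0.27 SD | 8.1% (11.7%) |
| 6:0 | 0.18 SD | 0.31 SD | 0.43 SD | 11.0% (17.7%) |
| 3:3 opposite | 0.20 SD | 0.33 SD | 0.46 SD | 13.4% (23.6%) |

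Type I error is simulated for an unadjusted two-sided 5% t-test (100,000 replicates). For scale, the standard error with 12 per arm is √(2/12) = 0.41 SD. At r = 0.5 the 4:2 bias is 0.24 of that, 6:0 is 0.75 and opposite 3:3 is 0.80.

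**A rule common to both arms.** Here the 6 lowest of the pooled 30 are lost (simulation, 200,000 replicates).

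- No true effect: bias about 0, type I error 5.0% at r = 0.5 and at r = 0.7.
- Assumed true effect of 0.5 SD: the completers' difference averages about 0.45 SD (r = 0.5) or 0.40 SD (r = 0.7). Training that raises growth also changes who stays, so the effect shrinks.

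**Adjustment for baseline words**, which section 6.3.2 plans. Assume a baseline-growth correlation of 0.5 and r = 0.5. At 6:0 the unadjusted 0.31 SD falls to about 0.23, 0.16 or 0.09 SD when loss correlates 0.25, 0.5 or 0.75 with baseline. The value 0.25 = 0.5 × 0.5 applies if loss relates to baseline only through growth.

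**Recovering checklists.** At 6:0, if 3 of the 6 are recovered at random, that arm has 12 infants and half of S_6 remains: 0.5 × (5.497/2)/12 = 0.11 to 0.12 SD, down from 0.31. Recovery at random is optimistic, since families who left selectively may also reply selectively.

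**The case against.** The strongest objection is that rewording the analysis set does little alone. An infant who stops attending has no closing UK-CDI and no week-8 or week-9 test, so is missing under either wording. This stands. The new wording keeps only infants who missed sessions but reached the final assessments, and the plan does not clearly exclude them now. Every bias figure above concerns lost outcomes, so most of the benefit comes from collecting the checklist.

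Second, the planned covariate may absorb much of the bias if loss is driven by initial language level. This also stands, and is why a range is shown. It does not help with loss driven by progress during training.

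Third, the 6:0 and mirror-image 3:3 patterns are extreme and nothing in the documents suggests them. That is fair; they mark the outer range, and 4:2 is small beside the standard error.

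Fourth, the plan already allows rescheduling and reports reasons, and section 6.3 says only that non-completers are not *fully* analysed. These soften the point, but section 6.3.2 has no such qualifier. Section 6.1, read literally, allows non-finishers' data to be used. A reader might suppose that a *not* was dropped there; the documents do not settle it, and the three sections need reconciling either way.

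**Conclusion.** The point holds as a conditional risk to Objective B. The analysis rule, the undefined completion and the timing of the checklist are in the documents. The sizes rest wholly on assumed inputs: roughly 0.1 to 0.3 SD unadjusted at correlation 0.5, less after adjustment, against a standard error of 0.41 SD.

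The documents do not support four stronger readings that a reader might infer:

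- *The comparison will be biased.* Nothing says how loss relates to growth in either arm, and the direction depends on who is lost.
- *Unequal numbers lost prove bias.* With no true effect, a common loss rule gives no bias even when chance splits the losses unevenly, and equal numbers lost for opposite reasons do give bias.
- *A common loss rule is harmless.* That holds only with no true effect; otherwise, if loss depends on growth, the effect is attenuated.
- *All primary objectives are affected.* The t-tests against chance (Objective A) and the follow-up comparison with UK norms (Objective C) are not between-arm comparisons and lie outside this point.

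The change should be made before data are seen. Confidence is medium, because the size cannot be learned from the documents.

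**What to change.** 1. In sections 6.3 and 6.3.2, replace the restriction, for the between-arm comparisons, with: *every randomised infant with the outcome, in the allocated arm, whatever number of sessions was attended.* Reconcile section 6.1 with it.
2. Ask parents of infants who stop attending without full withdrawal to complete the week-9 UK-CDI by post or online. This carries most of the bias reduction, for vocabulary only. It cannot recover the noun-extension tests, which need the child present, or data destroyed after full withdrawal (section 4.1.5).
3. Keep completers as a sensitivity analysis. Define completion before data are seen, including how a stopped session that is not rescheduled counts.
4. Report by arm the numbers lost, the reasons, the number of full withdrawals (as a count only) and the numbers tested in weeks 8 and 9.

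**Cost.** Little extra work. The estimate may be slightly diluted by infants who had little training, and some forms will be completed in a different setting. Items 1 and 2 probably both need an amendment under section 5.8, as they touch scientific value and study conduct. Section 5.7 does not permit planned deviations, so approval must come before use.
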